12.2 Treatment Phase

- A. Once the subject has signed the study informed consent form, has completed the screening/baseline assessments, and has met all inclusion and exclusion criteria, the subject can be scheduled to undergo Sonata treatment. The treatment shall be performed in accordance with the physician Instructions for Use. Treatment phase activities will generally occur in a single visit.
- B. Prior to the treatment, the subject will be given a "Subject Post-Treatment Kit", that will be comprised of the following
- Subject Discharge Instructions (Appendix L)
 - Subject Treatment Recovery Questionnaire, with instructions on how to complete and when to return to Investigational Site
 - Study follow-up schedule
 - Investigational site contact information

C. Pre-treatment Work-up

The following assessments will be performed at the time of preadmission testing such that results are available prior to treatment, to update status and to confirm that the subject remains a suitable candidate for the investigational treatment.

- 1) Vital signs (including temperature, pulse, blood pressure, height, weight)
- 2) Urine or serum hCG
- 3) Venous thromboembolism risk classification (Table 5 below) per ACOG Practice Bulletin 84 (Appendix E)
- 4) Birth control adherence
- 5) Concomitant medications

D. Thromboembolism prophylaxis

ACOG Practice Bulletin 84 “Prevention of Deep Vein Thrombosis and Pulmonary Embolism” defines suitable prophylaxis according to the patient risk classification. Risk classification is dependent in part on duration of the surgical procedure. Since it is not known at the beginning of the Sonata treatment whether or not the procedure will last more than 30 minutes, all subjects will be treated, at a minimum, with prophylaxis according to the Moderate Risk category as shown in Table 5. Subjects classified as High Risk must be treated with the corresponding prophylaxis. See Appendix F for complete guidelines.

Table 5 Risk Classification for Venous Thromboembolism (ACOG Page 84)

Level of Risk	Definition	Successful Prevention Strategies
Low	Surgery lasting less than 30 minutes in patients younger than 40 years with no additional risk factors	No specific prophylaxis; early and “aggressive” mobilization
Moderate	Surgery lasting less than 30 minutes in patients with additional risk factors; surgery lasting less than 30 minutes in patients aged 40–60 years with no additional risk factors; major surgery in patients younger than 40 years with no additional risk factors	Low-dose unfractionated heparin (5,000 units every 12 hours), low molecular weight heparin (2,500 units dalteparin or 40 mg enoxaparin daily), graduated compression stockings, or intermittent pneumatic compression device
High	Surgery lasting less than 30 minutes in patients older than 60 years or with additional risk factors; major surgery in patients older than 40 years or with additional risk factors	Low-dose unfractionated heparin (5,000 units every 8 hours), low molecular weight heparin (5,000 units dalteparin or 40 mg enoxaparin daily), or intermittent pneumatic compression device
Highest	Major surgery in patients older than 60 years plus prior venous thromboembolism, cancer, or molecular hypercoagulable state	Low-dose unfractionated heparin (5,000 units every 8 hours), low molecular weight heparin (5,000 units dalteparin or 40 mg enoxaparin daily), or intermittent pneumatic compression device/graduated compression stockings + low-dose unfractionated heparin or low molecular weight heparin Consider continuing prophylaxis for 2–4 weeks after discharge.

Modified from Geerts WH, Pineo GF, Helt JA, Bergqvist D, Lassen MR, Colwell CW, et al. Prevention of venous thromboembolism: the Seventh ACCP Conference on Antithrombotic and Thrombolytic Therapy. Chest 2004;126(suppl):338S–400S.

E. Sonata Treatment

- 1) The treatment shall be performed in accordance with the physician Instructions for Use. Highlights are provided below.
 - (a) The intent is for all clinically relevant fibroids to be ablated during a single treatment session.
 - (b) Coincidental removal of an intrauterine polyp up to a maximum diameter of 1.5 cm and type 0 fibroids < 1.0 cm is allowed.
 - (c) A small number of sponsor representatives (generally one to three individuals) may be present during the procedure to provide equipment support if needed as well as for proctoring and general observation.
- 2) **Treatment and Recovery Assessments**
The following data will be collected on the day of the treatment prior to discharge:
 - (a) Treatment location (e.g. ambulatory care center, operating room, etc.)
 - (b) Treatment time, defined as time the Sonata device is inserted transvaginally to the time it is removed after the last ablation
 - (c) Room time, defined as time subject enters room to time subject exits room
 - (d) Actual discharge time
 - (e) Time that subject would have been eligible for discharge based on treatment recovery status (eg, "discharge in AM" order written) if scheduling, site policy, or non-procedure related health issues extend hospitalization
 - (f) Anesthesia and procedure-related medications
 - (g) Record of fibroids treated/untreated ("Treatment Assessment")
 - (h) Video of intrauterine ultrasound captured during treatment
 - (i) Subject assessment of pain and tolerance to treatment and recovery
 - (j) Pain medication use during recovery
 - (k) Narcotic use during recovery
 - (l) Concomitant meds
- 3) **Discharge Instructions**
Subjects will be given complete discharge instructions and will be cautioned that nothing should be placed in the vagina for 2 weeks following the Sonata treatment

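### Protocol 12.2 D sets a Moderate floor for thrombosis prophylaxis because duration is unknown, but on the most natural reading of Table 5 that floor is enough only for women under 40 without additional risk factors

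*Protocol*

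**What the plan says.** Protocol 12.2 C has each subject classified for thromboembolism risk before treatment. The pre-treatment assessments "will be performed at the time of preadmission testing such that results are available prior to treatment".

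Protocol 12.2 D then gives the prophylaxis rule in four steps:

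- Duration matters: "Risk classification is dependent in part on duration of the surgical procedure".
- Duration is unknown: "it is not known at the beginning of the Sonata treatment whether or not the procedure will last more than 30 minutes".
- Hence the floor: "all subjects will be treated, at a minimum, with prophylaxis according to the Moderate Risk category as shown in Table 5".
- Above the floor: "Subjects classified as High Risk must be treated with the corresponding prophylaxis".

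Three clauses of Table 5 decide the case of a woman without additional risk factors. The Moderate row includes "surgery lasting less than 30 minutes in patients aged 40–60 years with no additional risk factors" and also "major surgery in patients younger than 40 years with no additional risk factors". The High row includes "major surgery in patients older than 40 years or with additional risk factors". Inclusion criterion 2 in Protocol section 4 L admits women aged 25 to 50.

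**The concern.** The floor exists to protect a woman whose procedure turns out to be long. For a woman of 40 to 50 without additional risk factors it adds nothing, because Table 5 already places her in Moderate when surgery is short. If a long procedure moves her up a row, the floor does not follow. A site could give a 45-year-old compression stockings alone and comply with the text, although the High row has no stockings-only option.

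Protocol 13.3 names this classification as the means of limiting thrombosis and embolism risk. Protocol 13.2 reports one death some days after treatment with an early version of the system, which the Medical Advisory Board thought might have been a late embolus from the procedure. A rule that carries this weight should point to one row for each woman.

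**Working it through.** There is no stated figure to reproduce. The check applies Table 5, as printed, to the eligible population.

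**1. How the clauses are worded.**

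| Row | Under 30 minutes | Major surgery |
|---|---|---|
| Low | 1 | 0 |
| Moderate | 2 | 1 |
| High | 1 | 1 |
| Highest | 0 | 1 |
| Total | 4 | 3 |

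That makes 4 + 3 = 7 clauses, none worded for surgery over 30 minutes. The Highest row needs an age above 60 and cannot apply here.

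**2. Three possible readings of a procedure over 30 minutes.**

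- *It counts as major surgery.* Passing 30 minutes then raises the class, and Moderate is the right answer for a woman under 40 without risk factors. This fits the reason that 12.2 D gives.
- *It is never major surgery.* No row of Table 5 covers it at any age, so the table itself does not yield Moderate for it.
- *The procedure is major surgery whatever its length.* Women over 40 then meet a High clause even when surgery is short, and the 30-minute reason has no work to do.

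The first reading is the most natural, but it remains an inference.

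**3. The rows on the first reading.**

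| Woman | Under 30 minutes | Over 30 minutes | Is the Moderate floor enough if long? |
|---|---|---|---|
| 25–39, no additional risk factor | Low | Moderate | Yes |
| Exactly 40, no additional risk factor | Moderate | No clause fits | Table does not say |
| 41–50, no additional risk factor | Moderate | High | One row short |
| 25–50, with an additional risk factor | Printed in both Moderate and High | High | One row short if the site used the Moderate clause |

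**4. What one row short means in practice.**

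- Moderate options: heparin every 12 hours, dalteparin 2,500 units, enoxaparin 40 mg, stockings, pneumatic compression = 5.
- High options: heparin every 8 hours, dalteparin 5,000 units, enoxaparin 40 mg, pneumatic compression = 4.
- Shared: enoxaparin 40 mg and pneumatic compression = 2.
- Moderate only: 5 − 2 = 3.

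**5. Age range concerned.** Eligible years of age: 50 − 25 + 1 = 26. Ages 41 to 50 are 10 of these, and age 40 makes 11. These are years of age, not shares of women. The available text gives no age mix, procedure times, risk-factor frequency or choice of prophylaxis, so no head count can be derived.

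**The case against.** **The floor may only be meant to rule out Low.** The Low row requires surgery under 30 minutes. If that cannot be assured, everyone moves at least to Moderate, and nothing needs to be called major surgery. This is a fair reading, and it stops one from saying that 12.2 D contradicts Table 5. It does not tell a site what to do for women aged 40 or over: the protocol says that class depends partly on duration, yet the floor leaves them in their short-surgery row.

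**The bulletin may settle the term.** Sites hold it as an appendix and we do not. This stands, and it is why the fix begins with a check.

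**The High Risk sentence may close the gap.** A site that expects a long procedure in a 45-year-old can classify her High, and High prophylaxis is then compulsory. But classification is made with duration unknown, and nothing tells the site to assume the longer case. If sites always did, women under 40 without risk factors would already be Moderate and the floor would be redundant. Two sites can treat the same woman differently and both comply.

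**Stronger inferences that the documents do not support.** A reader might infer that women over 40 are being under-treated. That is not shown: it needs a long procedure, a site that assumed a short one, and a Moderate-only option. A reader might also take the death in 13.2 as evidence that the floor failed. The death certificate listed myocardial infarction, there was no autopsy, the investigator judged the death unrelated to device and procedure, and the woman's age, procedure time and prophylaxis are not given.

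**Conclusion.** The point holds as a minor safety clarification. If a procedure over 30 minutes falls under the major-surgery clauses, the Moderate floor is adequate only for women under 40 without additional risk factors. It can be one row short for women aged 41 to 50, and for women of any eligible age with an additional risk factor whom a site placed under the first Moderate clause. Age exactly 40 without risk factors is left undecided.

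The practical gap is confined to three of the five Moderate options. It disappears wherever a site uses pneumatic compression or enoxaparin 40 mg. The conclusion rests on the inferred meaning of major surgery, so confidence is medium. On the other readings the shortfall is not established in this form, but 12.2 D would still be clearer if it named the row for a long procedure. No endpoint, sample size or analysis changes.

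**What to change.** First confirm how the bulletin (Appendix E) uses the term major surgery. If it agrees with the reading above, replace the sentence in 12.2 D that sets the floor, and the High Risk sentence after it, with:

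> Because duration cannot be known in advance, each subject is classified as if the procedure will exceed 30 minutes, using the major-surgery clauses of Table 5. Women under 40 with no additional risk factor receive at least a Moderate-row option. Women aged 40 or older, and women of any age with an additional risk factor, receive a High-row option. Pneumatic compression or enoxaparin 40 mg satisfies both rows.

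This also settles the case of age exactly 40 and the double listing of short surgery with risk factors, in each case on the cautious side. If the bulletin uses the term differently, state in 12.2 D which row applies to a procedure over 30 minutes.

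The cost is a few sentences, plus a change of practice at any site that uses a Moderate-only option for these women. Pneumatic compression alone meets the High row, so no anticoagulant is forced. The downside is that some women aged 40 to 50, or with a risk factor, whose procedure proves short will get one row more than Table 5 requires. The present floor already does the same for women under 40.

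Separately, a clerical correction: 12.2 D sends the reader to Appendix F for the guideline, but 12.2 C and the appendix list in section 22 place the bulletin at Appendix E; F is the menstrual diary.

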12.3 Follow-up Phase

- A. Follow-up visits will occur in accordance with Table 6 below. The day of the Sonata treatment represents Day 0. Study visits that do not occur within the below time windows will be considered protocol deviations.

Table 6 Follow-up (FU) Visit Windows

Visit	Allowed Visit Date Range
FU Visit 1 - 10 days	± 4 days
FU Visit 2 - 30 days	± 1 week
FU Visit 3 - 3 months	± 2 weeks
FU Visit 4 - 6 months	± 4 weeks
FU Visit 5 - 12 months	± 2 months
FU Visit 6 - 2 years	± 2 months
FU Visit 7 - 3 years	± 2 months

- B. The measurements and evaluations that will occur at each follow-up visit are provided below.

- 1) Follow-up Visit 1: 10 Days (± 4 days)
(Phone Call or visit at Investigator's discretion)

(a) Adverse Events

The primary purpose of Follow-up Visit #1 is to assess safety. Subjects will be asked if they have experienced any untoward medical occurrences since the Sonata treatment. If so, these events will be recorded on the Adverse Event case report form, in accordance with the procedures outlined later in this protocol.

(b) Post-treatment follow up

Subjects will be asked whether there is any change to their medical status. Subjects will be asked specifically if they have experienced any signs or symptoms of fibroid shedding: cramping, bleeding, passage of any tissue per vaginam.

(c) Concomitant Medications

Subjects will be asked about concomitant medications, noting in particular concomitant medications taken for the treatment of HMB.

(d) Adherence with/Continuance of Birth Control Method

Subjects will be asked if they are adhering to their chosen method of birth control, and if there have been any changes in their birth control method, including changes to medication type and preparation.

2) Follow-up Visit #2: 30 Days (\pm 1 week)

(a) Adverse Events

Subjects will be asked if they have experienced any untoward medical occurrences since the Sonata treatment. If so, these events will be recorded on the Adverse Event case report form, in accordance with the procedures outlined later in this protocol.

(b) Return to Normal Daily Activity

Subjects will be asked to submit their completed Treatment Recovery Questionnaire (Appendix C). Subjects who are not back to normal activity will be followed up by phone visits weekly until the subject has resumed normal activity or the reason for not resuming normal activity is not expected to change.

(c) Surgical Reintervention

Subjects will be asked if they have undergone any surgical procedure to treat their heavy menstrual bleeding. If so, the procedure performed and the date of the reintervention will be recorded.

(d) Concomitant Medications

Subjects will be asked about concomitant medications, noting in particular concomitant medications taken for the treatment of HMB.

(e) Pregnancy/Pregnancy Outcomes

Subjects will be asked if they have become pregnant since the last follow-up visit. If so, the subject will be released from all protocol specified follow-up assessments and visits, however the subject will be followed and pregnancy outcomes (including any complications) will be recorded as described in Section 10.6 of this protocol.

(f) Post-treatment follow up

Subjects will be asked whether there is any change to their medical status. Subjects will be asked specifically if they have experienced any signs or symptoms of fibroid shedding: cramping, bleeding, passage of any tissue per vaginam.

(g) Adherence with/Continuance of Birth Control Method

Subjects will be asked if they are adhering to their chosen method of birth control, and if there have been any changes in their birth control method, including changes to medication type and preparation.

Note: During follow-up visit #2, the subject will be given study materials in anticipation of follow-up visit #3, which will be comprised of the following:

- a copy of the EQ-5D Questionnaire (Appendix A). The EQ-5D should be completed during the subject's 3rd menstrual cycle post-treatment, preferably on the first full day of bleeding. It should be completed based solely on symptoms from that cycle.
- Menstrual diary (PBAC) with completion instructions noting that only the sanitary products provided should be used during the study while completing the PBAC.
- A supply of sanitary products in sufficient quantity to cover use for one menstrual cycle for the completion of the PBAC.

3) Follow-up Visit #3: 3 Months (\pm 2 weeks)

(a) UFS-QOL, EQ-5D, and WPAI:SHP Questionnaires

Subjects will be asked to return their completed EQ-5D questionnaire and will be asked to complete the UFS-QOL and WPAI:SHP questionnaires.

(b) Menstrual Diary

Subjects will be asked to return their completed menstrual diary (PBAC) for the menstrual cycle preceding the visit.

(c) Adverse Events

Subjects will be asked if they have experienced any untoward medical occurrences since the Sonata treatment. If so, these events will be recorded on the Adverse Event case report form, in accordance with the procedures outlined later in this protocol.

(d) Surgical Reintervention

Subjects will be asked if they have undergone any surgical procedure to treat their heavy menstrual bleeding. If so, the procedure performed and the date of the reintervention will be recorded.

(e) Pregnancy/Pregnancy Outcomes

Subjects will be asked if they have become pregnant since the last follow-up visit. If so, the subject will be released from all protocol specified follow-up assessments and visits, however the subject will be followed and pregnancy outcomes (including any complications) will be recorded as described in Section 10.6 of this protocol.

- (f) Amenorrhea
If the subject becomes amenorrheic, a pregnancy test (urine or serum hCG) will be performed and, if negative, a serum FSH level determination will also be obtained
- (g) Concomitant Medications
Subjects will also be asked about concomitant medications, noting concomitant medications taken for the treatment of excessive uterine bleeding.
- (h) Post-treatment follow up
Subjects will be asked whether there is any change to their medical status. Subjects will be asked specifically if they have experienced any signs of fibroid shedding: cramping, bleeding, passage of any tissue per vaginam.
- (i) Adherence with/Continuance of Birth Control Method
Subjects will be asked if they are adhering to their chosen method of birth control, and if there have been any changes in their birth control method, including changes to medication type and preparation.

Note: During follow-up visit #3, the subject will be given study materials in anticipation of follow-up visit #4, which will be comprised of the following:

- A copy of the EQ-5D Questionnaire (Appendix A). The EQ-5D should be completed during the subject's 6th menstrual cycle post-treatment, preferably on the first full day of bleeding. It should be completed based solely on symptoms from that cycle. If the subject has become amenorrheic, the EQ-5D may be completed at any time during the follow-up visit window.
- Menstrual diary (PBAC) with completion instructions noting that only the sanitary products provided should be used during the study while completing the PBAC.
- A supply of sanitary products in sufficient quantity to cover use for one menstrual cycle for the completion of the PBAC.

- 4) Follow-up Visits #4-5: 6 Months (\pm 4 weeks) and 12 Months (\pm 2 Months)
- (a) MRI (12 months only)
 - (b) UFS-QOL, EQ-5D, and WPAI:SHP Questionnaires
Subjects will be asked to return their completed EQ-5D questionnaire and will be asked to complete the UFS-QOL and WPAI:SHP questionnaires.
 - (c) Menstrual Diary
Subjects will be asked to return their completed menstrual diary (PBAC) for the menstrual cycle preceding the visit.
 - (d) Adverse Events
Subjects will be asked if they have experienced any untoward medical occurrences since the Sonata treatment. If so, these events will be recorded on the Adverse Event case report form, in accordance with the procedures outlined later in this protocol.
 - (e) Surgical Reintervention
Subjects will be asked if they have undergone any surgical procedure to treat their heavy menstrual bleeding. If so, the procedure performed and the date of the reintervention will be recorded.
 - (f) Pregnancy/Pregnancy Outcomes
Subjects will be asked if they have become pregnant since the last follow-up visit. If so, the subject will be released from all protocol specified follow-up assessments and visits, however the subject will be followed and pregnancy outcomes (including any complications) will be recorded as described in Section 10.6 of this protocol.
 - (g) Post-treatment follow-up
Subjects will be asked whether there is any change to their medical status. Subjects will be asked specifically if they have experienced any signs of fibroid shedding: cramping, bleeding, passage of any tissue per vaginam.
 - (h) Amenorrhea
If the subject becomes amenorrheic, a pregnancy test (urine or serum hCG) will be performed and, if negative, a serum FSH level determination will also be obtained.
 - (i) Concomitant Medications
Subjects will also be asked about concomitant medications, noting concomitant medications taken for the treatment of excessive uterine bleeding.

(j) Subject Satisfaction

Subjects will be asked to rate their satisfaction with the treatment, with responses based on a 6-point Likert scale ranging from “very satisfied” to “very dissatisfied”. They will also be asked if they would recommend the treatment to a friend with the same health problems using a 4-point scale from “definitely yes” to “definitely not”.

(k) Overall Treatment Effect (OTE)

Subjects will be asked to indicate whether their uterine fibroid symptoms have improved, remained the same, or worsened. If the subject indicates that her symptoms have improved, she will be asked to rate the degree of improvement on a 7-point scale from “almost the same, hardly better at all” (1) to “a very great deal better” (7). If the subject indicates that her symptoms worsened, she will be asked to rate the degree of worsening on a 7-point scale from “almost the same, hardly worse at all” (-1) to “A very great deal worse” (-7).

(l) Adherence with/Continuance of Birth Control Method

Subjects will be asked if they are adhering to their chosen method of birth control, and if there have been any changes in their birth control method, including changes to medication type and preparation.

Note: During follow-up visit #4, the subject will be given study materials in anticipation of follow-up visit #5, which will be comprised of the following:

- A copy of the EQ-5D Questionnaire (Appendix A). The EQ-5D should be completed during the subject’s 12th menstrual cycle post-treatment, preferably on the first full day of bleeding. It should be completed based solely on symptoms from that cycle. If the subject has become amenorrheic, the EQ-5D may be completed at any time during the follow-up visit window.
- Menstrual diary (PBAC) with completion instructions noting that only the sanitary products provided should be used during the study while completing the PBAC.
- A supply of sanitary products in sufficient quantity to cover use for one menstrual cycle for the completion of the PBAC.

- 5) Follow-up Visit 6 and 7: 2 and 3 years
(Phone Call or mail at Investigator's discretion)
- (a) UFS-QOL, EQ-5D, and WPAI:SHP Questionnaires
Subjects will be asked to return their completed EQ-5D questionnaire and will be asked to complete the UFS-QOL and WPAI:SHP questionnaires.
- (b) Pregnancy/Pregnancy Outcomes
Subjects will be asked if they have become pregnant since the last follow-up visit. If so, the subject will be released from any remaining protocol specified follow-up assessments and visits, however the subject will be followed and pregnancy outcomes (including any complications) will be recorded as described in Section 10.6 of this protocol.
- (c) Adverse Events
Subjects will be asked if they have experienced any untoward medical occurrences related to the abdomen and/or pelvis since the Sonata treatment. If so, these events will be recorded on the Adverse Event case report form, in accordance with the procedures outlined later in this protocol.
- (d) Surgical Reintervention
Subjects will be asked if they have undergone any surgical procedure to treat their heavy menstrual bleeding. If so, the procedure performed and the date of the reintervention will be recorded.
- (e) Subject Satisfaction
Subjects will be asked to rate their satisfaction with the treatment, with responses based on a 6-point Likert scale ranging from "very satisfied" to "very dissatisfied". They will also be asked if they would recommend the treatment to a friend with the same health problems using a 4-point scale from "definitely yes" to "definitely not".
- (f) Overall Treatment Effect (OTE)
Subjects will be asked to indicate whether their uterine fibroid symptoms have improved, remained the same, or worsened. If the subject indicates that her symptoms have improved, she will be asked to rate the degree of improvement on a 7-point scale from "almost the same, hardly better at all" (1) to "a very great deal better" (7). If the subject indicates that her symptoms worsened, she will be asked to rate the degree of worsening on a 7-point scale from "almost the same, hardly worse at all" (-1) to "A very great deal worse" (-7).

